10.1 Sample Size Considerations

With a sample size of approximately 20 patients in each cohort, a 95% confidence interval for the proportion of patients experiencing grade III-IV GVHD complications or unexplained prolonged myelosuppression complications in each cohort can be constructed to be within \pm 13.1% of the observed complication proportions. This calculation assumes an expected prevalence of each of these complication proportions of $\leq 10\%$.

Addendum November 2017 Extension of the UCB cohort

The preliminary results in the UCB cohort are encouraging (section 2.6). We therefore have increased accrual to this cohort to a total of **35 patients treated**. This will allow a preliminary assessment of efficacy. Patients who are enrolled but do not undergo treatment (defined as infusion of stem cell product) will be replaced.

Addendum May 2020: In order to further solidify outcomes in the CBU cohort and pending completion of next protocols, we will further increase accrual to this cohort to a total of **60 patients treated**. This will allow a definitive assessment of efficacy. Patients who are enrolled but do not undergo treatment (defined as infusion of stem cell product) will be replaced.

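### The CBU cohort was first enlarged because its own early results looked good; if response was among them, the pooled rate in 60 patients is expected to read a few points high, and no before/after display is planned

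*Combined protocol and SAP*

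**What the plan says.** Section 10.1 sizes the study for precision on complications: "With a sample size of approximately 20 patients in each cohort", the 95% interval is to lie within plus or minus "13.1% of the observed complication proportions". The basis is given too: "This calculation assumes an expected prevalence of each of these complication proportions of" at most 10%. Response does not enter that calculation.

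Two addenda then enlarge the CBU cohort only.

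- **November 2017:** "The preliminary results in the UCB cohort are encouraging (section 2.6). We therefore have increased accrual to this cohort to a total of". The new figure named there is "35 patients treated". The stated purpose is: "This will allow a preliminary assessment of efficacy".
- **May 2020:** the total rises to 60 treated, with a different reason: "In order to further solidify outcomes in the CBU cohort and pending completion of next protocols". The stated purpose is now: "This will allow a definitive assessment of efficacy".

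Both sizes are totals, so earlier patients count towards them. Neither addendum gives a reference rate, a target rate, a power or a precision.

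Response rate is a secondary objective (Section 1.2, item e). For secondary objectives, Section 10.2 plans binary proportions with 95% confidence intervals. It does not separate patients by stage of accrual and does not mention the 2017 look.

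**The concern.** When a cohort continues because its first patients did well, those patients are a selected group: on average their observed rate is above the true one, given that the cohort continued. Keeping them in the final total dilutes the excess without removing it, and an ordinary binomial interval takes no account of it.

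The likely excess is a few points. It matters because the remission rates cited in Sections 2.1 and following are low and close together: none, 14%, 20% and 30% in the table of patients failing hypomethylating agents, and 13% in the second-salvage series. A reader who sets a pooled rate, announced as definitive, against those figures could take a shift of 4 or 5 points for a treatment effect.

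**Working it through.** **1. The plan's own figure.** Wald half-width = 1.96 × √(p(1−p)/n). With p = 0.10 and n = 20: 1.96 × √(0.09/20) = 0.1315, or 13.15 points. The stated 13.1 reproduces. The sizes 35 and 60 have no stated derivation, so there is nothing to reproduce for them.

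**2. Inputs for the bias.** From Section 10.1: a planned first stage of about 20 and a final total of 60. The rest is assumed, because Section 2.6 (listed in the contents as the November 2017 preliminary results) is not in the text available: 20 patients assessed at the look, a true response rate p, and extension only if at least k of the 20 respond.

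**3. Formula.** Let X be the number of responders among the first 20, X ~ Bin(20, p). The 40 later patients are not selected by this look, so

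excess = (E[X | X ≥ k] + 40p)/60 − p.

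Example: p = 0.20, k = 6. P(X ≥ 6) = 0.196 and E[X | X ≥ 6] = 6.675, so the first 20 average 33.4%. Pooled: (6.675 + 8)/60 = 24.5%, an excess of 4.5 points.

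**4. Results, in percentage points at 60 patients.**

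| True rate | k = 5 | k = 6 | k = 7 |
|---|---|---|---|
| 20% | 3.1 | 4.5 | 5.9 |
| 25% | 2.2 | 3.3 | 4.6 |
| 30% | 1.4 | 2.3 | 3.4 |
| 50% | 0.06 | 0.19 | 0.46 |

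The last row is small because those bars are nearly always cleared at 50% (probability 0.94 to 0.99), so passing them selects little.

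**5. Sensitivity to the assumed look.** Taking 10, 15 or 20 patients at the look, true rates of 14 to 50%, and a bar between the true rate and 20 points above it, the excess runs from 1.3 to 7.5 points. The bar moves with the true rate here, so the small values in the 50% row do not carry over.

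**6. The interval.** At p = 0.20 and k = 6, the exact 95% interval on the pooled 60 covers the truth 91.7% of the time given extension, and essentially all misses lie on the favourable side (lower limit above the truth 8.3% of the time, against 2.2% without selection). With the bar at the true rate (k = 4), the excess is 2.0 points and coverage is 96.3%.

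**7. Excess against sampling error.** Half-widths for true rates of 14 to 30%:

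- all 60 patients: 8.8 to 11.6 points;
- the last 40: 10.8 to 14.2 points;
- the last 25 (those beyond the first 35): 13.6 to 18.0 points.

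The excess stays inside the pooled half-width in every single-look scenario above.

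**8. Averaged over both outcomes.** In the example, cohorts that are not extended average (4 − 0.196 × 6.675)/0.804 = 3.35 responders of 20, or 16.7%. Over both outcomes the mean is 0.196 × 24.5% + 0.804 × 16.7% = 18.2%, about 1.75 points below the true 20%. The upward bias is therefore conditional on extension.

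**The case against.** **What was encouraging is not shown.** The primary objective is safety, so the word could refer to few cases of severe GVHD or prolonged myelosuppression. Response would then be biased only as far as it correlates with safety, and the complication rate would be the one pulled, downwards. This stands. The addendum's next sentence speaks of efficacy, which makes response plausible but not certain. Nor can it be said that the plan omits the number of patients at the look, since Section 2.6 may give it.

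**A reader might infer that both enlargements were driven by results.** The documents do not support that. The step to 60 is justified by firming up outcomes while later protocols are prepared, and the only status reported with it, in Section 10.2, is that stopping rules had not been met. The figures above use the 2017 look alone.

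**A reader might also infer that the pooled rate is biased upward without qualification.** It is not: step 8 shows a slight downward bias over all possible courses. But the extension did take place, so the conditional case is the one that applies to this cohort.

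**The size rests on assumed inputs.** This stands. The 5.9-point end needs an event of about 9% probability (at least 7 of 20 at a true rate of 20%).

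**Later patients may differ for other reasons.** In May 2020 eligibility wording was added on failure of targeted agents and venetoclax (Section 3.1), and the GVHD section changed (5.5). An early/late difference could reflect this as well as selection, so the later group should stand beside the pooled estimate and not replace it.

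**The analysis is descriptive.** Section 10 plans no efficacy test and no formal comparison with the cited series. This limits the consequence, but it does not fit well with calling the result definitive.

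**Conclusion.** The point holds in a limited, conditional form. By the protocol's own account the November 2017 enlargement followed from the cohort's results, and those patients remain in the total of 60. If response was part of what was encouraging, the pooled response rate is expected to be too high given extension. The excess is about 1.4 to 5.9 points for 20 patients at the look, a true rate of 20 to 30% and a bar of 5 to 7 responders; it is below 0.5 points at a true rate of 50% with the same bars. In these scenarios it is smaller than the half-width of the pooled interval. The May 2020 step is not shown to depend on results. This is a minor reporting matter that does not invalidate the pooled estimate, but the pooled figure should not be presented as definitive without the staged display.

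**What to change.** In Sections 10.1 and 10.2:

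- State that response rate with its 95% interval will be reported for patients treated before and after the November 2017 decision, beside the pooled estimate. Give the number assessed at the decision.
- Show the same split at May 2020, descriptively, with the number assessed then and a note that eligibility and GVHD wording changed at that time.
- State that the pooled figure includes the patients who prompted the extension, and that the post-November 2017 estimate is free of that particular selection. The split adds this estimate; it does not correct the pooled one.
- Replace the promise of a definitive efficacy assessment with descriptive wording.

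The cost is a few sentences and extra table columns, using data already collected. The later group's interval is wider: a half-width of about 11 to 14 points if 40 patients follow the look, against about 9 to 12 for all 60 (true rates 14 to 30%). Its figure may also be less favourable.

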5.2 Stem Cell Source and Cell Dose

Within 72 hours after completion of the chemotherapy regimen, and no sooner than 24 hours after administration of the last dose of chemotherapy, umbilical cord graft or haplo-graft will be administered.

Supportive care and premedications for stem cell administration will be governed by current policies of transplant program.

The choice between CBU vs Haplo-graft will be based on availability according to the table below. It may be further influenced by practical issues such as insurance approval etc.

Graft selection algorithm		
1	CBU Unit 5/6 Matched	1 NIMA match with patient
2	CBU Unit 5/6 Matched	Shared IPA target(s) with patient
3	Haplo Identical relative	
4	CBU Unit 4/6 matched	1-2 NIMA matches with patient
5	CBU Unit 4/6 matched	Shared IPA target(s) with patient

5.3 CBU UNIT The CBU unit must supply a minimum of $0.5 \times 10^7/\text{kg}$ and a maximum of $2.5 \times 10^7/\text{kg}$ nucleated cell dose pre-cryopreservation. The unit must match at a minimum of 4 of 6 at HLA-A, -B antigens, -DRB1 alleles with the recipient. Mismatches (0-2) can be at any loci -. Although molecular level typing will be available for the patient and the CBU unit, a match is defined at intermediate resolution for HLA-A and -B and at high resolution for -DRB1. The CBU donor will also have undergone HLA typing of the mother, thus allowing determination of the CBU-IPA and NIMA.

CBU grafts used in this study will be investigational units that meet all criteria for clinical use. Better matching units will be preferred over less matching units as long as the CBU dose exceeds $0.5 \times 10^7 \text{ NBC/kg}$

ALL RECIPIENTS SHOULD HAVE TESTING FOR CLASS I AND CLASS II HLA ANTIBODIES. IF ANTIBODIES ARE PRESENT, CBU SHOULD BE CHOSEN THAT ARE NOT TARGETED. THIS MAY REQUIRE DQ AND DP TESTING OF THE CBU.²⁵⁻²⁷

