9.0 CRITERIA FOR STUDY EVALUATION

- Responses must be maintained with no evidence of AML/MDS for more than four weeks. If chemotherapy continues, there can be no evidence of relapse within four weeks. Response assessments will require a bone marrow aspirate to be performed. In the event of a dry tap or an aspiration that is inadequate for interpretation, a bone marrow biopsy is required for response assessment.
- **Complete Remission (CR):** Complete remission is defined as all of the following:

- Peripheral Blood Counts:
 - Absolute neutrophil count $\geq 1000/\mu\text{L}$
 - Platelet count $\geq 100,000/\mu\text{L}$

- No leukemic blasts in the peripheral blood
 - Adequate erythroid recovery so that RBC transfusions are not necessary
- Bone Marrow:
 - Adequate cellularity
 - No Auer rods
 - < 5% blast cells
- No extramedullary leukemia (such as CNS or soft tissue involvement)

OR

- Complete Response with Incomplete Platelet Recovery (CRp): CRp satisfies all CR criteria except platelets < 100,000/ μ L, but platelet transfusions are not necessary
- **Partial Remission (PR):** Must meet all criteria of a CR except that the bone marrow may contain 5%-24% blasts
- **Treatment Failure:** Failure to achieve a CR (by 60 days after initial induction therapy started)
 - Treatment Failure Due to Resistant Disease:
 - Patients treated appropriately
 - Survived > 30 days after therapy began.
 - Failed to achieve remission due to persistent AML as determined by peripheral blood and bone marrow aspirate and biopsy.
 - Treatment Failure Due to Death of the Patient:
 - Patient died within 30 days of starting protocol therapy.
 - Record whether the patient died with or without evidence of persistent leukemia as determined by peripheral blood and bone marrow aspirate and biopsy.
- **Relapse** - Any of the following, occurring after either CR, CRp, or PR:
 - The reappearance of circulating blast cells not attributable to “overshoot” following recovery from myelosuppressive therapy
 - > 5% blasts in the marrow, not attributable to another cause (e.g., CSF, bone marrow regeneration)
 - Development of extramedullary leukemia

- **Toxicities will be followed using CTCAE criteria.**
Most toxicities will be attributable to the chemotherapy. Toxicity attributed to the cell infusions may include occurrence of GVHD and unexpected duration of myelosuppression. Severity of myelosuppression (hematologic toxicity) will not be taken into account.
- **Time to neutrophil recovery:**

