10.3 Screening vs Treating

We anticipate that several patients will be consented and then screened for each patient treated. The sample sizes are based on number of patients treated – not on number of patients consented.

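### The plan ties its efficacy claim to 60 infused patients and replaces those who miss infusion, without reconciling this with a failure definition that starts at induction

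*Combined protocol and SAP*

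**What the plan says.** **Accrual and efficacy (Section 10.1).** The May 2020 addendum states: "we will further increase accrual to this cohort to a total of 60 patients treated". It says of this increase: "This will allow a definitive assessment of efficacy". Both addenda carry the same replacement rule: "Patients who are enrolled but do not undergo treatment (defined as infusion of stem cell product) will be replaced".

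**Sample-size basis (Section 10.3).** "The sample sizes are based on number of patients treated – not on number of patients consented". The same section expects attrition: "We anticipate that several patients will be consented and then screened for each patient treated".

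**Timing of infusion (Section 5.2).** The graft is given "Within 72 hours after completion of the chemotherapy regimen, and no sooner than 24 hours after administration of the last dose of chemotherapy". All of the induction chemotherapy therefore comes before the event that makes a patient count as treated.

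**Failure (Section 9.0).** Treatment failure is "Failure to achieve a CR (by 60 days after initial induction therapy started"). One of its categories, failure due to death, is defined as "Patient died within 30 days of starting protocol therapy". The definition of treatment-related mortality in the same section also starts with the preparative regimen.

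**Analysis (Sections 1.2 and 10.2).** Response is a secondary objective, summarised as a proportion with a 95% confidence interval. No analysis set is named for it, and no null rate or test is given.

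**The concern.** Sections 9.0 and 10.1 treat the same patient differently. Take someone who enrols, starts induction and dies on day 6. Under Section 9.0 this is a treatment failure. Under Section 10.1 the patient was never treated and is replaced. If the response rate is then taken over the 60 infused patients, this failure leaves the denominator.

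Such losses are unlikely to be random. Section 10 itself describes reinduction in these patients as very toxic, with high induction-related mortality. Those who die or deteriorate before infusion would seldom have responded. The infused-only rate would then overstate what a patient starting the strategy can expect, under an addendum that calls the efficacy assessment definitive.

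**Working it through.** **The plan's own figure.** The only computed design figure is the ±13.1 points in Section 10.1 for a complication rate of 10% with n = 20: 1.96 × √(0.10 × 0.90 / 20) = 0.1315. It reproduces, but it concerns safety. No calculation accompanies n = 35 or n = 60.

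**General form.** Let f be the share of patients who start induction but are not infused, r the response rate in the infused and q the rate in non-infused starters.

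- All-starter rate = (1 − f) r + f q
- Infused-only rate minus all-starter rate = f (r − q)

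The bias is upward if q < r, and zero if f = 0 or q = r.

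**Effect for a range of f.** The documents give no f, so 5% to 30% is an assumption. The 30 responders among 60 infused are illustrative. Starters = 60 / (1 − f), rounded up to whole patients.

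| Assumed f | Starters | Rate, non-infused all failures | Rate, non-infused respond at 13% |
|---|---|---|---|
| 5% | 64 | 30/64 = 46.9% | 30.52/64 = 47.7% |
| 10% | 67 | 30/67 = 44.8% | 30.91/67 = 46.1% |
| 20% | 75 | 30/75 = 40.0% | 31.95/75 = 42.6% |
| 30% | 86 | 30/86 = 34.9% | 33.38/86 = 38.8% |

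Rounding up matters a little in the first row: 4/64 is 6.3%, and an exact 5% would give 0.50 × 0.95 = 47.5%. The 13% is the complete remission rate in the 594-patient second-salvage series in Section 2.1, used only as a plausible non-zero value for q.

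**Against sampling error.** For 30/60 the exact 95% interval is 36.8% to 63.2%, and the approximate half-width is 1.96 × √(0.25 / 60) = 12.7 points. At f = 10% the shift is about 5 points, well inside that. At f = 30% it is about 15 points, outside it.

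**Early death alone.** Assumptions: 10 days from start of induction to infusion (a 7-day regimen, one of the examples in Section 5.1, plus 72 hours) and exponential survival with median m months. Deaths before infusion = 1 − 2^(−10 / (30.4 m)).

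- m = 5.6 (longest median in the Section 2.1 table): 4.0%. A 30% rate becomes 0.30 × 0.960 = 28.8%.
- m = 1.5 (second-salvage series): 14.1%. A 30% rate becomes 0.30 × 0.859 = 25.8%.

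The largest shift is 4.2 points. The half-width at 30% with n = 60 is 1.96 × √(0.21 / 60) = 11.6 points.

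**The case against.** **The denominator is inferred.** Sections 10.1 and 10.3 govern accrual. Replacing a patient does not by itself remove that patient from analysis, and Section 11.1 keeps patients removed from protocol therapy in follow-up for survival and disease status. This stands: infused-only analysis is the natural reading, not a stated rule. But nothing in the available text settles the matter, and Section 9.0 points the other way.

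**The infused set answers a fair question.** Objective 1.2(e) asks about response after each treatment, and Section 8.1 identifies the infusion as the investigational component. This stands too, and is why the infused set should be kept as one efficacy set. One could also argue that protocol therapy begins with the infusion. However, Section 5 lists induction as the first element of the treatment plan, and the 60-day failure clock explicitly starts with induction.

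**No benchmark comparison is planned.** A reader might infer that the trial will be judged against the 0% to 30% remission rates in Section 2.1 and that the comparison is unfair. The documents do not support this. Those rates appear as background, Section 10.2 plans description only, and the table does not describe its denominators. The treatment groups of the second-salvage series do sum to its total (74 + 30 + 171 + 73 + 246 = 594), so that series appears to count everyone treated, but no test against it is specified.

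**Section 10.3 does not show heavy loss after induction starts.** A reader might take several consented patients per treated patient as evidence of a large f. That sentence refers to consent and screening, and Section 4.1 places HLA typing and graft identification at enrolment. Losses before chemotherapy are not part of this bias, and no split is given.

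**The size is assumed.** Induction is the physician's choice, a constant hazard is a simplification, and eligibility requires a Karnofsky score of at least 70. The bias may be only a few points. Section 2.6, on preliminary results, was not available for this review and may hold enrolled and infused counts, so these are not treated as missing.

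**Conclusion.** The point holds in a limited form. The plan counts accrual by infusion, replaces enrolled patients who miss it and rests an efficacy claim on the infused, while its failure definition starts at induction. The two are not reconciled. If response is computed over the infused only, it is probably biased upward. This requires that some patients start induction without being infused, and that they respond less often than the infused.

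The size cannot be fixed from the available text. It is at most about 4 points at a 30% rate on the early-death assumptions, and about 3 to 15 points at a 50% rate for f of 5% to 30% if no non-infused starter responds. The first could be lost in sampling error; the upper end of the second could not. The documents do not support saying that early failures are certainly excluded, or that a planned benchmark comparison is invalid. This is an inexpensive improvement to make, not a flaw that undermines the safety objective.

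**What to change.** - Keep the infused patients as the safety population and as one named efficacy set.
- Add a second efficacy set: all enrolled patients who began protocol induction. Time response from the start of induction, consistent with Section 9.0, and count non-infused patients as non-responders. If survival is reported, start it at the same point.
- State in Section 10.1 that replacement affects accrual only and does not remove a patient who started induction from this second set.
- Report the numbers consented, started on induction, infused and replaced, with reasons, separating losses before chemotherapy from losses after it starts.
- Describe the efficacy assessment as descriptive rather than definitive.

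**Cost.** Revised wording, one more table and a slightly less favourable rate. No extra infused patients are needed. Outcomes of non-infused starters must be collected. Because the visit schedule in Section 7.1 is anchored to infusion, the sponsor should confirm that these data exist for patients already enrolled.

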10.2 Stopping Rules

The occurrence of adverse events that are life-threatening, lead to ICU admission or death (as defined in section 8.3) will lead to temporary suspension of enrollment and immediate assessment of events.

The study will also be paused if there is death that is directly attributed to infusion of adoptive cell therapy; for example severe infusion related reaction, infection from contaminated unit, Grade 5 GVHD etc.

Enrollment may resume upon assessment by the investigators that there are no safety issues and upon appropriate revision of the protocol – if required.

After 10 patients are enrolled in each group, the incidence of the above-defined life-threatening complications will be assessed. If more than one patient out of 10 enrolled patients (i.e., $>10\%$) in a cohort experiences either of these complications, the cohort will be stopped for safety. Each cohort will be evaluated separately with respect to these complications. Additionally, if three or more of the first five patients in a particular cohort experiences either of these complications, the cohort will also be stopped. This is illustrated in the Table below.

N treated subjects	5	10	15	20
No with gr III-IV GVHD to trigger stopping rules	2	2	3	4
No with prolonged myelosuppression to trigger stopping rules	2	2	3	4
No with either Gr III-IV GVHD or with prolonged myelosuppression to trigger stopping rules	3			

For assessment of secondary objectives, descriptive statistics will be utilized via the method of binary proportions and 95% confidence intervals will be calculated to assess the precision of the obtained estimates. All analyses will be performed in SAS Version 9.3 (SAS Institute, Inc., Cary, NC) and Stata Version 13.0 (StataCorp, College Station, TX).

Addendum 5/26/2020: To date stopping rules have not been met in the CBU cohort after enrolling more than 30 patients. The Haplo cohort has not accrued.

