13.0 DATA SAFETY MONITORING BOARD

The Weill Cornell Medical College Data Safety Monitoring Board (DSMB) is being requested to review safety data and to make recommendations regarding continuation, termination, or modification to the study.

The research team will report all adverse events to the DSMB after accrual of successive sets of five patient to each arm of the protocol. The report to the DSMB will include a description of adverse events attributed to cell infusion and of patient's outcome.

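### The count-based stopping rule in section 10.2 is read only at fixed looks, so patients can be infused after a stop is already certain

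*Combined protocol and SAP*

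**What the plan says.** Section 10 restricts the counted complications to grade III-IV GVHD and unexplained prolonged myelosuppression, and describes both as life threatening.

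Section 10.2 then gives three things that bear on timing.

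- **Text rule.** "After 10 patients are enrolled in each group, the incidence of the above-defined life-threatening complications will be assessed". The cohort stops "If more than one patient out of 10 enrolled patients" has either complication. In addition, "if three or more of the first five patients in a particular cohort experiences either of these complications, the cohort will also be stopped".
- **Table.** The columns are "N treated subjects" at 5, 10, 15 and 20. The rows "No with gr III-IV GVHD to trigger stopping rules" and "No with prolonged myelosuppression to trigger stopping rules" each read 2, 2, 3, 4. A third row pools the two complications and has one entry: 3 at n = 5.
- **Suspension clause.** Events that are life-threatening, fatal or lead to ICU admission, with a cross-reference to section 8.3, "will lead to temporary suspension of enrollment and immediate assessment of events". Enrollment restarts when the investigators judge that there is no safety issue.

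Section 13.0 has the DSMB receive reports "after accrual of successive sets of five patient to each arm of the protocol". The May 2020 addendum to 10.2 records that the CBU cohort had enrolled more than 30 patients without meeting a stopping rule, and that the haplo cohort had no patients.

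**The concern.** The rule acts on cumulative counts, which can only stay level or rise. Once the count equals the trigger for the next look, the result of that look is known. As written, the cohort still runs on to the look. Under the table, a second grade III-IV GVHD case in patient 6 fixes the stop at 10, yet patients 7 to 10 can be infused. Under text and table together, one GVHD case and one myelosuppression case in two of the first five patients does not stop the cohort at five, but it already exceeds one affected patient out of 10.

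Safety is the primary objective, and section 2.5 relies on these rules to guard against excess toxicity. Infusions given after the decision is fixed expose patients without adding anything to that decision.

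**Working it through.** **The plan's own figure.** Section 10.1 states a 95% interval half-width of 13.1% with about 20 patients at 10%. Check: 1.96 × √(0.10 × 0.90 / 20) = 0.1315, which agrees apart from rounding. The documents give no operating characteristics for the stopping rule.

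**Inputs.** Looks and triggers are from 10.2. A 10% rate is the plan's own limit (section 10); 20% and 30% are assumptions. Patients are independent, each outcome is known before the next infusion, and no event-driven pause applies.

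**Table rule, one complication, p = 0.10.** The second event falls in patient t with probability (t − 1) p² (1 − p)^(t − 2).

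| t | Probability | Look that stops | Infused after t |
|---|---|---|---|
| 2 | 0.0100 | 5 | 3 |
| 3 | 0.0180 | 5 | 2 |
| 4 | 0.0243 | 5 | 1 |
| 5 | 0.0292 | 5 | 0 |
| 6 | 0.0328 | 10 | 4 |
| 7 | 0.0354 | 10 | 3 |
| 8 | 0.0372 | 10 | 2 |
| 9 | 0.0383 | 10 | 1 |
| 10 | 0.0387 | 10 | 0 |

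- Stops: 0.0815 at look 5 and 0.1824 at look 10. The same method gives 0.0345 at 15 (trigger 3) and 0.0155 at 20 (trigger 4). Total 0.314.
- Expected further infusions: 0.0903 (look 5) + 0.3502 (look 10) + 0.0525 (looks 15 and 20) = 0.493.
- Mean per stopped cohort: 0.493 / 0.314 = 1.57.

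Repeating this at other rates:

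| True rate | P(stop) | Mean further infusions per stopped cohort | Stopped cohorts with at least one | Expected number infused: at looks → at trigger |
|---|---|---|---|---|
| 10% | 31.4% | 1.6 | 72% | 16.8 → 16.3 |
| 20% | 74.4% | 1.7 | 75% | 12.1 → 10.8 |
| 30% | 94.2% | 1.8 | 79% | 8.8 → 7.1 |

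The maximum is 4. P(stop) is the same whether the stop comes at the look or at the trigger.

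**Text and table read together, 10% for each complication, independent.** Any affected patient: 1 − 0.9² = 0.19. Three affected patients with two possible complications must include two with the same one, so the operative test at five is two of the same type.

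- Stop at 5: 1 − (1 − 0.0815)² = 15.6%.
- Stop by 10 (two or more affected of 10, p = 0.19): 59.3%, so 43.7% stop at 10.
- Further infusions after the second affected patient: mean 2.5 per stopped cohort. The maximum is 8, which needs patients 1 and 2 to have different complications and no second event of either type by patient 5.
- At a 30% combined rate, split equally, the mean is 2.6.

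**Effect of delay.** The documents give no accrual rate. Assume that L patients are infused before the deciding outcome is known; the avoidable number is then max(k − L, 0), where k is the overshoot. With L = 2 the means fall to 0.4 (table, one complication, 10%) and 1.0 (text and table). With L = 4 they are 0 and 0.3.

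**Does the suspension clause cover the counted events?** Section 10 calls both complications life threatening, which would bring each under the clause. Section 8.3, to which the clause refers, gives immediate reporting to fatal or ICU events and to fatal or grade IV acute GVHD. Non-fatal grade III GVHD without ICU admission, and time to hematopoietic recovery, fall in its quarterly column. The two readings conflict, and neither ties restart to the count.

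**The case against.** The strongest case against is that other safeguards already act between looks. If section 10's description governs, every counted event suspends enrollment and is assessed at once. Investigators score inpatients weekly (section 12), and the DSMB, which can recommend termination, hears after every five patients. This stands in part: the right statement is that patients can be infused after the stop is certain. A reader might infer that they necessarily will be, and the documents do not support that. But the suspension is temporary, its scope is ambiguous, and restart rests on investigator judgement.

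A reader might also take the text alone and conclude that any two affected patients among the first five let the cohort continue, giving a mean of 3.4 further infusions per stopped cohort at a 19% combined rate. The table does not allow this, since it stops at five on two of the same complication. At 10% each, about 55% of cohorts with exactly two affected in the first five would stop there. That is why the mean falls to 2.5.

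Delay is a further fair objection. Myelosuppression cannot be declared until more than 30 days after chemotherapy, and GVHD is assessed weekly to day 60. Immediate stopping cannot recover infusions given while outcomes are pending.

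Finally, a reader might infer that CBU patients were infused after a stop was due. The addendum says that the rules had not been met in that cohort, which had passed every listed look.

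**Conclusion.** The point holds as a gap in the rule's wording: the count rule is tied to fixed looks, has no instruction to stop when the trigger is reached, and is not reliably backed by the suspension clause. The size is modest. It is about 1.6 to 1.8 further infusions per stopped cohort under the table for one complication at true rates of 10% to 30%, and about 2.5 with text and table together at 10% each. These rest on independent outcomes, immediate knowledge and no pause, and are upper limits on what can be saved. The exposure is the haplo cohort. For CBU, the gap would return only if a boundary were written beyond 20 treated, where the table has none although the target is 60. The change is worth making before the first haplo infusion.

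**What to change.** 1. Reconcile the boundaries in 10.2 first. The text pools the two complications; the table counts them separately from 10 onward. The choice matters: with 10% for each, the chance of stopping by patient 10 is 59% pooled and 1 − (1 − 0.264)² = 46% counted separately. The wording on timing should not settle this by default.
2. Then add: *Counts are updated after every event; a cohort stops as soon as the number of affected patients reaches the applicable trigger for the next look, without waiting for that look to fill.* The looks remain the points at which the trigger changes. If the reconciled trigger can fall between looks, as in the text (three of five, then two of 10), refer instead to the lowest trigger among the remaining looks.
3. State whether every counted complication invokes the suspension clause, bring 10.2 and 8.3 into line on this, and make restart conditional on the count being below the trigger.

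The cost is a short amendment to 10.2, with a matching edit to 8.3 if needed. Applied to the reconciled boundary, item 2 stops the same cohorts, only sooner, so the probability of stopping does not change. It does not deal with outcomes still pending.
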